5.5. Demographic and Clinically Specific Subgroups

All the primary, secondary, and safety analyses will be performed by gender, race, and ethnicity to determine if the treatment effect or safety differs by these demographics. Patient-specific clinical or "severity" factors/categories and treatment categories will be explored. Planned explorations include age, GCS (or NIHSS), ICH location, time to treatment, and initial ICH size.

Subgroups utilized for adaptive cut points are: age <56, age 56 through 67, and age \geq 67; GCS 3–8, 9– 12 and 13–15; initial ICH size (0–<25; 25–<35; 35–<45; 45–<55; 55–<65; and \geq 65). We will examine the following subgroups: stability ICH size <50 and \geq 50; lobar vs. deep; stability IVH size; time to surgery at <24 hours, 24-48 hours, and >48 hours from ictus; GCS 3–8, 9–12 and 13–15; and age <65 and \geq 65.

Additional analysis of groupings of these clinical factors will be dictated by group size and balance between groups. We will also explore time as a continuum and at other clinically meaningful cut points. We will treat age, ICH size, and IVH size as a continuum and collapse them to other meaningful subgroups, as described above. NIHSS and GCS will also be treated as a continuum of scores. Based on post hoc analysis of the STICH trials, we will evaluate GCS 9–12 versus all other score levels.

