ischemic stroke, with stable clinical and functional performance occurring at 180 to 365 days. Surgical subjects achieved good functional outcomes more frequently than medical subjects, despite having a slightly worse initial ICH volume severity (34 mL vs. 43 mL), GCS score (12 vs. 11), and IVH size (2 mL vs. 4 mL). At 180 days, 35% of surgical subjects had reached mRS 0-3 compared to 24% in the medical group. When analyses were adjusted for initial severity imbalance, the effect increases. MISTIE II was amended to following the mRS 4, 5

subjects through 365 days. The differential benefit for the mRS 0-3 state increases to 14% and a significant proportion of mRS 0,1 and 2 states are observed in the surgical group where the difference between surgery and medical is also 14% (Fig. 3). Thus, an improvement across all levels of mRS appears to be associated with the MIS+rt-PA group and is consistent over time, with an important proportion reaching high degrees of independence. MISTIE III will confirm the reproducibility, size and generalizability of the benefit previously observed in the MISTIE II proof-of-concept trial. Subgroup analysis suggests no effect of location (deep vs. lobar), size, time to surgery or age (Fig. 4).

[figure not shown]

**Figure 4.** Multivariable analysis of severity factors. Analysis of factors other than catheter location within the clot in Stage 1 did not identify any other significant factors that could account for variation. This resulted in the simplification of instructions for the surgical task in Stage 2 regarding optimal catheter placement.

**Surgical Performance and Functional Benefit:** A

range of clot size reductions occurred in the surgical group. Several reasons exist for this finding. Despite having set the goal of >80% clot reduction from the animal studies to the MISTIE II subjects, this goal was not well achieved at the MISTIE II sites in Stage 1. Initial evaluation of factors associated with clot size reduction suggests that the precision of the catheter

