## 4 SELECTION AND ENROLLMENT OF SUBJECTS

### 4.1 Inclusion Criteria

4.1.1 Spontaneous supratentorial ICH  $\geq 30$  mL measured by the site utilizing ABC/2 method using radiographic imaging (CT, CTA, etc.), with a GCS  $\leq 14$  or a NIHSS  $\geq 6$ .

4.1.2 Stability CT scan done at least 6 hours after diagnostic CT showing clot stability (growth  $< 5$  mL as measured by ABC/2 method).

If the clot volume measured on this stability CT scan increases by 5 mL or more, a second stability determination is allowed by repeat CT scan at least 12 hours later. Additional scans are permitted as needed every 12 hours to continue to monitor for stability up until the eligibility time window closes. Subsequent clot retraction remains inclusionary as long as the ICH clot size remains  $\geq 25$  mL.

4.1.3 Symptoms less than 24 hours prior to diagnostic CT (dCT) scan. An unknown time of onset is exclusionary. Use the time the patient was last known to be well for patients that awaken from sleep with symptoms.

4.1.4 Ability to randomize between 12 and 72 hours after dCT.

4.1.5 SBP  $< 180$  mmHg sustained for six hours recorded closest to the time of randomization.

4.1.6 Historical Rankin score of 0 or 1.

4.1.7 Age  $\geq 18$  and older.

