2.2. Efficacy Measures Summary: All Analyses Adjusted Similarly to the Primary Analysis

- **Primary Efficacy Analysis:** Dichotomized, adjudicated, cross-sectional mRS 0-3 vs. 4-6 at 365 days post-ictus, adjusting for baseline (pre-randomization) variables used in covariate adaptive randomization as well as the clinically established severity variables IVH size and ICH location (lobar or deep).
- Additional, Exploratory Analyses of mRS at 365 days:
 - a. Dichotomized, adjudicated, cross-sectional mRS 0-3 vs. 4-6 at 365 days post ictus, adjusting for baseline (pre-randomization) variables used in covariate adaptive randomization as well as additional baseline variables determined to be associated with the outcome.
 - b. Ordinal, adjudicated mRS (0-6) at 365 days.
 - c. mRS 0-3 vs. 4-6 at 365 days based on a full longitudinal analysis of the mRS data at 90, 180, and 270 days.
 - d. Severity subgroup analyses (including, but not limited to, IVH size, location of ICH, presentation co-morbidities such as diabetes, CVD, and white matter disease, etc.)
 - e. Cross-sectional of mRS 0-3 vs. 4-6 for demographic subgroups of patients, including for race and gender. (For d and e, see section 5.5.)
 - f. Analysis of cross-sectional mRS 0-3 vs. 4-6 at 365 days that models random effects for hospital sites.

• Secondary Analyses of other outcomes

- 1. Dichotomized eGOS UGR-US vs. LS-Death at 365 days.
 - Subordinate: Ordinal eGOS UGR, LGR, MD, LM, US vs. LS, VS, Death at 365 days.
- 2. All-cause mortality longitudinally from ictus to 365 days.
 - Subordinate: Predictors of mortality.
- 3. Relationship between clot removal as an AUC clot-assessment that estimates the timeweighted clot volume from ictus to end of treatment (EOT; i.e., 24 hours after last dose) as AUC clot exposure and functional outcome (proportion 0-3 mRS).
- 4. Patient disposition:
 - a. Home days over 365 days' time from ictus.
 - b. Patient location at 365 days post ictus (i.e., good vs. bad location. See Tertiary 2g for definition.)
- 5. 180-day efficacy:
 - a. Dichotomized, adjudicated, cross-sectional mRS 0-3 vs. 4-6.
 - Subordinate (1): Ordinal, adjudicated mRS (0-6).
 - b. Dichotomized, adjudicated eGOS UGR, LGR, MD, LM, US vs. LS, VS, Death.
 - Subordinate (2): Ordinal, eGOS UGR, LGR, MD, LM, US vs. LS, VS, Death.
 - Subordinate analyses 2-5 as defined under the Primary but for eGOS.
- 6. Type and intensity of ICU management:
 - a. ICU days

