Minimally Invasive Surgery Plus rt-PA for ICH Evacuation Phase 3

- b. ICU management (ICP, Ventilation, BP support, osmotherapies)
- c. Hospital days
- 7. EQ-VAS and EQ-5D

• Tertiary (exploratory/sensitivity):

- 1. Functional status at 180 and 365 days post-stroke:
 - a. GOS
 - b. Barthel Index
 - c. NIHSS
 - d. MMSE
- 2. Quality of life at 180 and 365 days post-stroke:
 - a. SIŚ
 - b. PBSI
 - c. Personal Health Utility Assessment Interview
 - d. CES-D
 - e. EQ dimensions individually assessed
 - f. Home days (180 only)
 - g. Patient location including proportion of days in home, rehabilitation, acute care, longterm care facilities. These will be evaluated by individual location type and dichotomized as good vs bad outcome defined as home and rehabilitation vs acute care, long-term care and death.
 - h. Proportion of subjects in vegetative condition
- 3. Cost-benefit model

In addition to the primary, secondary, and tertiary (exploratory) measures, there are a number of related and intermediate surrogate outcomes of interest, including time to treatment, surgical task descriptors, clot locations, Glasgow Coma Scale (GCS), Graeb Scale, clot lysis rate and final clot size reduction.

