2.3. Safety

The safety of MIS+rt-PA relative to medical management is assessed by comparing the proportion of subjects between the two groups with treatment-related SAEs within the 30-day time frame: mortality, rebleeding, infection, and first-week (designated as operative mortality for the surgical group) mortality. Additionally, the number and proportion of all SAEs across the entire time frame in the respective randomized groups will be evaluated starting with the follow-up time frames of 180 and 365.

Interim safety analyses will be prepared for the external Data Safety and Monitoring Board (DSMB) on a pre-arranged schedule (such as semi-annual or after enrollment of a fixed number of subjects) to evaluate efficacy and safety. Safety measures include: monitoring the incidence of symptomatic and asymptomatic intracranial bleeding events (i.e., hemorrhage extension, new hemorrhage, catheter-tract hemorrhage) through daily computed tomography (CT) scans for the first four days after randomization and then repeated one day (approximately 24 hours) after ICH catheter removal, and monitoring the incidence of confirmed and suspected infection and in-hospital mortality.

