2.3.1. Safety Measures Summary

- Mortality and safety events at 30 days post-randomization:
 - a. First-week (operative) mortality
 - b. All-cause mortality

- c. Symptomatic bleeding rate
- d. Infection rate
- e. Total SAEs at 30 days
- f. Summary of AEs and SAEs by MedDRA code and grouped by organ system

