14.0. Safety Analyses

14.1. Mortality and Safety Events at 30 Days Post Randomization

The primary safety measures for this study are symptomatic intracranial bleeding, infection, and 30-day mortality. The safety thresholds for these measures have been set as: 30-day mortality >60%, a MIS+rt-PA–related symptomatic bleeding rate >25% (occurring during active treatment or during the 72 hours after treatment will be monitored), first-week operative death rate >10%, and a procedure-related infection rate >15% (over the initial 30 days). Bleeding will be further characterized as during the exposure to dosing of alteplase and the subsequent 72 hours. Comparisons to medical subjects in the same time frame will be made. Total SAEs at 30 and 180 days, as well as summary of AEs and SAEs by MedDRA code and grouped by organ system, will be compared by treatment groups.

Statistical Hypothesis: Early use of MIS+rt-PA for 3 days for the treatment of ICH is as safe as medically managed ICH, measured by rates of procedure-related mortality, rebleeding, and infection within 30 days post-randomization. The null hypothesis is: *Early use of MIS+rt-PA is worse than medical management for a specific safety measure.*

Analysis: The number of SAEs will be tabulated by SAE type post-stroke for the total population as well as by treatment group, with particular emphasis placed on group differences at 30 days post-randomization. Any treatment group differences in SAEs enumerated for interim analyses will remain blinded to investigators associated with this study. Unmasked results (e.g., group A versus B, where the labels "A" and "B" are randomly assigned to the surgical and medically managed groups) will be made available only during the closed sessions of DSMB meetings.

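### Time to surgery is listed as a subgroup factor although medical subjects have no such time, and the 30-day safety comparison is worded both with and without a relatedness limit

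*SAP*

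**What the plan says.** **Timing.** SAP 5.5 names the subgroups to be examined. Among stability ICH size, lobar or deep location, IVH size, GCS and age stands "time to surgery at <24 hours, 24-48 hours, and >48 hours from ictus". The same section lists time to treatment among its planned explorations. SAP 2.2 items d and e, the severity and demographic subgroup analyses of 365-day mRS 0-3 vs. 4-6, point to that list: "For d and e, see section 5.5". Neither document says what value a medical subject takes, which medical subjects form the comparator, or that the analysis stays within the surgical arm.

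**Safety, with a relatedness limit.** SAP 2.3 assesses safety by "comparing the proportion of subjects between the two groups with treatment-related SAEs within the 30-day time frame". The hypothesis in SAP 14.1 is "measured by rates of procedure-related mortality, rebleeding, and infection within 30 days post-randomization". Protocol 9.1 (Efficacy Measures Summary, secondary measure 3) and Hypothesis 1b in protocol 9.1.7.a also specify procedure-related mortality.

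**Safety, without one.** Protocol 1.2 compares rates of mortality, rebleeding and infection at 30 days. SAP 2.3.1 lists "All-cause mortality", symptomatic bleeding, infection and total SAEs. The primary safety measures that open SAP 14.1, and the 10% margins later in that section, carry no relatedness condition.

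Protocol 10.4.2 defines relatedness only to the MIS procedure or the rt-PA administrations.

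**The concern.** A treatment-effect subgroup needs a variable that is fixed at randomization and observed in both arms. Time to surgery is neither. Protocol 4.3.6 allows the operation to be postponed after randomization, with stability rechecked first, so the time reflects both scheduling and the patient's course. Setting surgical time bands against any medical group mixes timing with selection. Timing claims of this kind are a realistic product: protocol 2.2 already reports for phase II that "Subgroup analysis suggests no effect of location (deep vs. lobar), size, time to surgery or age".

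For safety, the two wordings are different estimands for a primary objective. A medical subject who receives neither MIS nor rt-PA cannot have a related event. A related-only comparison therefore has an essentially empty control arm and becomes a cap on one arm's attributed events. It is easier to pass, and it could miss an excess of deaths that an all-cause comparison would show. If the text is left as it stands, someone must choose between the wordings at analysis.

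**Working it through.** **Timing: what exists in both arms.**

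1. Protocol 4.1 requires symptoms less than 24 h before the diagnostic CT and "Ability to randomize between 12 and 72 hours after dCT". Time from ictus to randomization therefore runs from about 12 h to about 24 + 72 = 96 h. It is known for every subject, because an unknown onset time is exclusionary.
2. Time to surgery exists only for subjects who are operated on. No figure in the documents gives control-arm outcome by time, so the size of any distortion cannot be computed.

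**Safety: inputs.** 250 per arm (SAP 2.1); pass if the upper one-sided 95% bound on the rate difference is at most 10% (SAP 14.1). The one stated figure on these inputs is the 88% power for 25% vs 38%. It reproduces:

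- pooled SE = sqrt(2 × 0.315 × 0.685 / 250) = 0.04155
- unpooled SE = sqrt((0.25 × 0.75 + 0.38 × 0.62) / 250) = 0.04114
- (0.13 − 1.96 × 0.04155) / 0.04114 = 1.18, which gives 88.1%

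The SAP states no power or boundary for the safety tests, so these were worked out directly.

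**Safety: formula.** Upper bound = (ps − pc) + 1.645 × sqrt(ps(1 − ps)/250 + pc(1 − pc)/250).

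| Deaths, surgical vs medical | Difference | SE | Upper bound | Result |
|---|---|---|---|---|
| 37 vs 25, all causes | 4.8% | 2.94% | 9.64% | pass |
| 38 vs 25, all causes | 5.2% | 2.96% | 10.07% | fail |
| 18 vs 0, related only | 7.2% | 1.63% | 9.89% | pass |
| 19 vs 0, related only | 7.6% | 1.68% | 10.36% | fail |

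At 38 vs 25 deaths, the all-cause test fails, while the related-only test passes whenever 18 or fewer of the 38 surgical deaths (47%) are attributed to MIS or rt-PA. Phase II 30-day mortality of 15% vs 10% (protocol 2.2, Mortality) would correspond to 37.5 vs 25 deaths, which is at this boundary.

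**The case against.** **The operative safety text is already arm-neutral.** A reader might infer that the between-arm safety comparisons rest on relatedness. They do not. SAP 2.3.1, the primary safety measures, the margins, and the Fisher comparison of all AEs and SAEs in SAP 14.3 can be counted in both arms. Even SAP 2.3 goes on to name first-week mortality, called operative only for the surgical group, and then all SAEs in both groups. SAP 14.2 sits under total SAEs and adds disease-associated events, so it is not a related-only test, although it gives no criteria for mortality attributed to medical management. This objection stands. What remains is a conflict between the introductory and hypothesis wording and the operative endpoints.

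**A disagreement rate would be too strong.** A reader might take the phase II rates as true and compute how often all-cause fails while related-only passes. By exact enumeration the answer is 48% of trials if up to 20% of surgical deaths are attributed, 46% at 30%, 34% at 40% and 14% at 50%. The share is an assumption, and the rates come from 54 and 42 patients with no mortality difference noted. Protocol 10.4.2 does not expect events more than 7 days after MIS to be related, which points to a low share. However, one of the two early phase II deaths was a postoperative myocardial infarction, so those deaths do not settle it.

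**Time to surgery may be meant descriptively.** SAP 5.5 also speaks of treatment categories, item d in SAP 2.2 does not name timing among its examples, and SAP 8.0 treats analyses without hypotheses as exploratory. That reading is available, but it is not stated. A few medical subjects might have a salvage craniotomy time, which is not a comparable quantity.

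**The two SAP lists do not contradict each other.** A reader might see a clash because SAP 2.2 counts time to treatment among "related and intermediate surrogate outcomes of interest, including time to treatment, surgical task descriptors". The same list contains GCS and clot locations, which are also subgroup factors in SAP 5.5, so appearing in both places shows nothing.

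**Conclusion.** Both parts hold as matters of specification.

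For timing, the plan names a post-randomization variable that exists in one arm as a subgroup factor for a between-arm outcome, with no comparator. The analysis is exploratory, and the size of the possible distortion cannot be derived from the documents.

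For safety, the SAP and protocol each word the comparison in two ways that can give opposite answers near the margin, as 38 vs 25 deaths shows. That example assumes 250 analysed per arm, the normal-approximation bound and no related events in the medical arm. It illustrates that the wording matters; it does not estimate how often it would matter.

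The primary efficacy analysis and the sample size are unaffected. The text should be settled before the arms are compared.

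**What to change.** **Timing.** In SAP 5.5, define the treatment-effect subgroup by time from ictus to randomization. SAP 5.5 already plans to explore time as a continuum, so make this one exploratory treatment-by-time interaction. Report time to surgery and time to treatment descriptively within the surgical arm only. The cost is low power. With a median split (125 per cell, 25% vs 38%), the SE of a risk difference is 0.0582 and of the difference between two is 0.0823, so 80% power needs 2.80 × 0.0823, about 23 points. With time kept continuous, the SE is 0.0411 per SD, so 80% power needs 0.115 per SD. Between the means of the two halves this is about 18 points if times are normal (1.596 SD) and 20 if uniform (1.732 SD). Both distributions are assumptions.

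**Safety.** Reword SAP 2.3, the SAP 14.1 hypothesis, SAP 14.2, protocol 9.1 (secondary measure 3) and protocol Hypothesis 1b to match protocol 1.2, SAP 2.3.1 and the SAP 14.1 margins. The between-arm non-inferiority tests should count all deaths, symptomatic bleeds and infections from randomization to day 30, regardless of attributed relatedness. Tabulate relatedness for the surgical arm only, and keep it for the suspension triggers.

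No new data are needed, but the edit reaches the protocol as well as the SAP. Counting all events dilutes procedure-specific harm, which is why the surgical-arm table must stay. The all-cause test is not unduly strict: with 10% mortality in both arms, SE = sqrt(2 × 0.09 / 250) = 0.0268 and 0.10 / 0.0268 − 1.645 = 2.08, so it passes in 98% of trials.

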5.6. Definition of Treatment Failures

Treatment failures are defined as: rt-PA administrations discontinued due to clinically significant rebleeding (prolonged GCS motor deterioration >2 motor points), the Investigator's judgment to not treat, and failure to achieve the target volume of 15 mL or less.

6.0. Randomization

Randomization will occur after completed screening for vascular malformation and central validation of inclusion and exclusion criteria. Subjects will be randomized to MIS+rt-PA or medical management using a covariate-adaptive design similar to that used for the CLEAR III trial.² The goal of this randomization scheme is to obtain an improved balance across study arms in the number of subjects with certain prerandomization variables that are most strongly predictive of the functional outcomes (mRS) at 180 and 365 days post-stroke. These variables include pre-randomization clot volume, age, and baseline severity of impairment as measured by GCS. Under this scenario, a randomization scheme will be used which increases a newly enrolled subject's probability of being assigned to the study arm that improves the overall balance in these important prognostic factors. Briefly, prior to randomization for each incoming patient, the imbalance between treatment arms will be determined using the accumulating available data on clot volume, age and GCS. The patient will then be randomized with high probability (e.g., "weighted coin toss") to the treatment arm that lowers the imbalance. Patients at any given site will not be considered for covariate-adaptive randomization until the site has enrolled four or six (blinded; sites are randomized to four or six to maintain blinding) patients into each treatment arm by within-site block randomization. This randomization scheme will be implemented using software included in the MISTIE III EDC (electronic data capture) system similar to what has been successfully implemented in the CLEAR III trial.

7.0. Blinding

The examiner performing the 30-, 180-, and 365-day follow-up assessments will video record the mRS interview assessments and upload the video to the Outcome CCC at the Western Infirmary in Glasgow, UK, where trained reviewers will classify the interview objectively without knowledge of the examiner's

score, patient name, or the treatment details including therapy intensity levels.

8.0. Multiplicity

The primary analysis of efficacy is tested at the two-sided alpha level of 0.05. In addition, secondary analyses will consider the alpha=0.05 two-sided type I error. Secondary analyses will be examined in the order specified and will not be corrected for multiplicity of testing.

Secondaries 2-7 are defined. The other analyses without specific hypotheses are considered exploratory. We will present descriptive statistics and CIs.

For safety outcomes, we do not account for multiplicity as this study was not powered to observe safety. Thus, a cautionary approach is justified.

9.0. Missing Data

Based on previous MISTIE and CLEAR studies performed in this group of stroke patients, the CCC will make substantial efforts to ensure complete collection of data for all patients, and to accrue minimal loss to follow-up (LTF) to optimize evaluation of the primary outcome of 365-day adjudicated mRS post-stroke. The CLEAR III trial experienced an overall LTF rate of 2%. Since we expect missingness will be more prevalent for the 365-day mRS (the primary efficacy end point) than at early time points, we will use the targeted maximum likelihood estimator (TMLE)³ to adjust for censoring, as specified in the description of the model for the primary efficacy model given in Section 11.1 below. The effects of incompleteness/noncompliance will be quantified through sensitivity analyses, the gold standard in the field.⁴

